13.1. General Considerations

- One SAS program will be created for each output.
- Each output will be stored in a separate file.
- Output files will be delivered in Word format.
- Numbering of TFLs will follow ICH E3 guidance.

13.2. Table, Listing, and Figure Format

13.2.1. General

- All TFLs will be produced in landscape format on *American letter size / A4 paper size*, unless otherwise specified.
- All TFLs will be produced using the Courier New font, size 8 which is the smallest acceptable point size for the Regulatory Authorities.
- The data displays for all TFLs will have a minimum blank 1-inch margin on all 4 sides. Note: No headers or footers from Stats programming to be present in this area. This blank area is required to add additional Publishing text and lines during Final CSR Publishing.
- Headers and footers for figures will be in Courier New font, size 8 which is the smallest acceptable point size for the Regulatory Authorities.
- Legends will be used for all figures with more than 1 variable, group, or item displayed.
- TFLs will be in black and white (no color), unless otherwise specified.
- Specialized text styles, such as bolding, italics, borders, shading, and superscripted and subscripted text, will not be used in the TFLs, unless otherwise specified. On some occasions, superscripts 1, 2, or 3 may be used (see below).
- Only standard keyboard characters will be used in the TFLs. Special characters, such as non-printable control characters, printer-specific, or font-specific characters, will not be used. Hexadecimal-derived characters will be used, where possible, if they are appropriate to help display math symbols (e.g., μ). Certain subscripts and superscripts (e.g., cm₂, C_{max}) will be employed on a case-by-case basis.
- Mixed case will be used for all titles, footnotes, column headers, and programmer-supplied formats, as appropriate.

13.2.2. Headers

- All output should have the following header at the top left of each page:
- Scynexis, Inc. Protocol SCY-078-206

- Draft/Final Run
- All output should have Page n of N at the top or bottom right corner of each page. TFLs are internally paginated in relation to the total length (i.e., the page number should appear sequentially as page n of N, where N is the total number of pages in the table).
- The date output was generated should appear along with the program name as a footer on each page.

13.2.3. Display Titles

Each FL are identified by the designation and a numeral. (i.e., Table 14.1.1). A decimal system (x.y and x.y.z) are used to identify TFLs with related contents. The title is centered. The analysis set are identified on the line immediately following the title. The title and table designation are single spaced. A solid line spanning the margins will separate the display titles from the column headers. There will be 1 blank line between the last title and the solid line.

Table x.y.z
First Line of Title
Second Line of Title if Needed
(ITT Analysis Set)

13.2.4. Column Headers

- Column headings are displayed immediately below the solid line described above in initial upper-case characters.
- In the case of efficacy tables, the variable (or characteristic) column will be on the far left followed by the treatment group columns and total column (if applicable). P-values may be presented under the total column or in separate p-value column (if applicable). Within-treatment comparisons may have p-values presented in a row beneath the summary statistics for that treatment.
- For numeric variables, include “unit” in column or row heading when appropriate.
- Analysis set sizes will be presented for each treatment group in the column heading as (N=xx) (or in the row headings, if applicable). This is distinct from the ‘n’ used for the descriptive statistics representing the number of subjects in the analysis set.
- The order of treatments in the tables and listings will be Placebo first in the case of placebo controlled studies and Active comparators first in the case of active comparator trials, followed by a total column (if applicable).

13.2.5. Body of the Data Display

13.2.5.1. *General Conventions*

Data in columns of a table or listing are formatted as follows:

- Alphanumeric values are left-justified;
- Whole numbers (e.g., counts) are right-justified; and
- Numbers containing fractional portions are decimal aligned; and

- Mixtures of whole numbers and numbers containing fractional portions are center aligned.

13.2.5.2. Table Conventions

- Units will be included where available
- If the categories of a parameter are ordered, then all categories between the maximum and minimum category are presented in the table, even if n=0 for all treatment groups in a given category that is between the minimum and maximum level for that parameter. For example, the frequency distribution for symptom severity would appear as:

Severity Rating	N
severe	0
moderate	8
mild	3

Where percentages are presented in these tables, zero percentages will not be presented and so counts of 0 will be presented as 0 and not as 0 (0%).

- If the categories are not ordered (e.g., Medical History, Reasons for Discontinuation from the Study, etc.), then only those categories for which there is at least 1 subject represented in 1 or more groups are included.
- An Unknown or Missing category are added to each parameter for which information is not available for 1 or more subjects.
- Unless otherwise specified, the estimated mean and median for a set of values are printed out to 1 more significant digit than the original values, and standard deviations are printed out to 2 more significant digits than the original values. The minimum and maximum should report the same significant digits as the original values. For example, for systolic blood pressure:

n	XX
Mean	XXX.X
Std Dev	X.XX
Median	XXX.X
Min	XXX
Max	XXX

- P-values are output in the format: “0.xxx”, where xxx is the value rounded to 3 decimal places. Every p-value less than 0.001 will be presented as <0.001. If the p-value are less than 0.0001, then present as <0.0001. If the p-value is returned as >0.999, then present as >0.999.
- Percentage values are printed to one decimal place, in parentheses with no spaces, one space after the count (e.g., 7 (12.8%), 13 (5.4%)). Values that round down to <1% will be displayed as '<1'. Unless otherwise noted, for all percentages, the number of subjects in the analysis set for the treatment group who have an observation will be the denominator. Percentages after zero counts should not be displayed and percentages equating to 100% are presented as 100%, without decimal places.
- Tabular display of data for medical history, prior/concomitant medications, and all tabular displays of adverse event data are presented by the body system, treatment class, or SOC with the highest occurrence in the ibrexafungerp + Voriconazole treatment group in decreasing order, assuming all terms are coded. Within

the body system, drug class and SOC, medical history (by preferred term), drugs (by ATC code), and adverse events (by preferred term) are displayed in decreasing order. If incidence for more than 1 term is identical, they should then be sorted alphabetically. Missing descriptive statistics or p-values which cannot be estimated are reported as “-”.

- For categorical summaries (number and percentage of subjects) where a subject can be included in more than one category, describe in a footnote or programming note if the subject are included in the summary statistics for all relevant categories or just 1 category and the criteria for selecting the criteria.
- Where a category with a subheading (such as system organ class) has to be split over more than one page, output the subheading followed by “(cont)” at the top of each subsequent page. The overall summary statistics for the subheading should only be output on the first relevant page.

13.2.5.3. *Listing Conventions*

- Listings will be sorted for presentation in order of treatment groups as above, subject number, visit/collection day, and visit/collection time.
- Missing data are represented on subject listings as either a hyphen (“-”) with a corresponding footnote (“- = unknown or not evaluated”), or as “N/A”, with the footnote “N/A = not applicable”, whichever is appropriate.
- Dates are printed in SAS DATE9.format (“ddMMMyyyy”: 01JUL2000). Missing portions of dates are represented on subject listings as dashes (--JUL2000). Dates that are missing because they are not applicable for the subject are output as “N/A”, unless otherwise specified.
- All observed time values are to be presented using a 24-hour clock HH:MM or HH:MM:SS format (e.g., 11:26:45, or 11:26). Time will only be reported if it was measured as part of the study.
- Units will be included where available.

13.2.5.4. *Figure Conventions*

- Unless otherwise specified, for all figures, study visits will be displayed on the X-axis and endpoint (e.g., treatment mean change from Baseline) values will be displayed on the Y-axis.

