The largest randomized controlled study evaluating antifungal combination therapy for patients with IPA was reported by Marr K et al. in 2015.⁷ This study assessed the safety and efficacy of voriconazole and anidulafungin compared with voriconazole monotherapy for the treatment of IPA. The study included 454 patients with hematological malignancies or hematopoietic stem cell transplantation and suspected or documented IPA and the primary analysis was done in 277 patients with documented IPA. Although the study failed to demonstrate statistically significant improvement in all-cause mortality with the combination therapy when compared with monotherapy, there was a clear trend towards improved survival in the group receiving combination therapy. Overall mortality rates at 6 weeks were 19.3% (26 of 135) for combination therapy and 27.5% (39 of 142) for monotherapy (difference, - 8.2 percentage points [95% CI, - 19.0 to 1.5]; P = 0.087).

Most patients (218 of 277 [78.7%]) had a diagnosis of IPA established by radiographic findings and mycological evidence in the form of galactomannan positivity. In a post hoc analysis of this dominant subgroup, 6-week mortality was lower in combination therapy than in monotherapy (15.7% [17 of 108] vs. 27.3% [30 of 110]; difference, -11.5 percentage points [CI, -22.7 to -0.4]; P= 0.037). A limitation of this study was that anidulafungin is only available intravenously (IV), thus limiting its use for long-term administration as often needed in IPA patients, resulting in a median duration of the combination therapy of 14 days.

SCY-078 antifungal activity

The spectrum and potency of activity of SCY-078 has been evaluated by numerous independent laboratories against an extensive panel of clinically relevant yeast and mold isolates using the Clinical and Laboratory Standards Institute (CLSI) and European Committee on Antimicrobial Susceptibility Testing (EUCAST) methods. Overall, the epidemiological studies have demonstrated that SCY-078 has potent, broad-spectrum activity against the majority of the clinical isolates tested. These studies have laid the foundation in support of the use of SCY-078 for the treatment of invasive fungal infections.

In vitro activity against Candida spp.

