6.3. Missing Data

Data from subjects who withdraw will be included, where possible, in all summaries and analyses.

For the efficacy analyses, subjects who do not have an EoT assessment will be assigned an indeterminate outcome, so will be classed as treatment failures for the corresponding efficacy analyses. For subjects who withdraw from the study early, every effort will be made to collect EoT visit information at the point of withdrawal.

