8.1. Key Efficacy Endpoint and Analysis

The key efficacy endpoint is the assessment of Global Response as determined by the DRC.

The DRC will assess the Global Response at Day 42, Day 84 and EoT.

Analysis of Global Response by the DRC will be for the ITT Population.

Global Response will be summarized at each visit.

In addition, the percentage of subjects with a Global Response, defined as either a complete or partial response at EoT, Day 42 and Day 84 will also be summarized. Subjects with missing data at EoT, Day 42 and Day 84 will be considered as indeterminate response at the corresponding visit. The response rate will be calculated for each treatment group as the number of successes divided by the total number of patients (success + failure + indeterminate).

The difference in response rates between treatments will be presented along with a 95% confidence interval (CI) calculated using the wmethod of Clopper-Pearson.

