8.2.5. Percentage of Subjects with Target Changes in GMI from Baseline

The percentage of subjects with the following target reductions in serum GMI from baseline will be presented at Weeks 1, 2, 4 and 6:

- Fifty percent reduction or greater
- Twenty-five percent reduction or greater
- Any percent reduction
- Reduction equal to or greater than 0.25
- Reduction to < 0.5

The difference in rates between treatments will be presented along with a 95% CI calculated using the method of Clopper-Pearson.

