8.2.10. Percentage of Subjects with Target Changes in Serum β -D-Glucan from Baseline

The percentage of subjects with the following target changes in serum β -D-glucan from baseline will be presented at Weeks 1, 2, 4 and 6 for the ITT Population:

- Fifty percent reduction or greater
- Twenty-five percent reduction or greater
- Any percent reduction
- Negative serum β -D-glucan

The difference in rates between treatments will be presented along with a 95% CI calculated using the method of Clopper-Pearson.

8.2.11. Percentage of Subjects that Convert from Positive Plasma *Aspergillus* PCR at Baseline to Negative

The percentage of subjects that convert from positive plasma *Aspergillus* PCR at baseline to negative will be presented at Weeks 1, 2, 4 and 6 for the ITT Population.

The difference in rates between treatments will be presented along with a 95% CI calculated using the method of Clopper-Pearson.

8.2.12. Absolute Change in Karnofsky Score from Baseline to Days 42 and 84

Karnofsky Performance Status is assessed at screening, Day 1, Day 14, Day 28, Day 42, Day 56, Day 70 and Day 84.

Karnofsky Performance Status will be summarized as a categorical variable at each visit.

In addition, taking Karnofsky Performance Status as a continuous variable, absolute change from baseline in Karnofsky score will be summarized, by treatment, for the ITT Population at Day 42 and Day 84.

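### By-visit responder percentages for serum GMI, beta-D-glucan and PCR count only subjects with an observation, so subjects who died or stopped treatment leave the comparison although Global Response keeps them in

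*SAP*

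**What the plan says.** SAP 13.2.5.2 gives the rule: "the number of subjects in the analysis set for the treatment group who have an observation will be the denominator". The opening words of the same sentence set its reach: "Unless otherwise noted, for all percentages, the number of subjects in the analysis set".

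The three biomarker sections do not replace it:
- SAP 8.2.5 (GMI): "The percentage of subjects with the following target reductions in serum GMI from baseline will be presented at Weeks 1, 2, 4 and 6". It gives no population, denominator or rule for death or a missing sample.
- SAP 8.2.10 (beta-D-glucan): "from baseline will be presented at Weeks 1, 2, 4 and 6 for the ITT Population".
- SAP 8.2.11 (PCR conversion): "to negative will be presented at Weeks 1, 2, 4 and 6 for the ITT Population".

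Naming the ITT population in the last two does not override the default, which already operates within an analysis set. All three sections present a between-arm difference with a 95% CI.

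The general missing-data rule in SAP 6.3 is tied to one visit: "subjects who do not have an EoT assessment will be assigned an indeterminate outcome". It does not reach Weeks 1, 2, 4 and 6.

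Where a full denominator was wanted, the SAP wrote one. SAP 8.1 defines the Global Response rate as "number of successes divided by the total number of patients (success + failure + indeterminate"), and 8.2.7 and 8.2.8 carry that analysis to clinical, mycological and radiological response.

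**The concern.** Death and discontinuation for lack of efficacy (a listed reason in Protocol 12.3) are outcomes of the disease under treatment. Removing those subjects turns the biomarker percentage into a rate among survivors who are still sampled. The arms are then no longer compared as randomised. If one arm keeps more very sick subjects alive, they enter its denominator, while their counterparts in the other arm have left.

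Stopping treatment matters as well as death. Under SAP 8.2.4, GMI after Day 14 is taken every 14 days during treatment, then at EoT and follow-up. The Day 42 contact table lists no GMI. Unscheduled assessments are not summarized (SAP 6.1) and visit windows are not used (SAP 6.4), so an early EoT sample does not fill a missing Week 4 or Week 6 value. A subject who stops early for success can therefore also disappear.

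At stake is the use of these results. Protocol 19.7.1 names GMI decrease among the three main efficacy measures, Protocol 19.1 makes preliminary effect sizes the main goal, and Protocol 8.2 expects the study to guide endpoint choice for Phase 3.

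**Working it through.** The documents give no responder rate, power or sample-size calculation, so there is no planned figure to reproduce. The check compares the two denominators.

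**Inputs**
- Six-week mortality in the combination trial cited in Protocol 8.1: "19.3% (26 of 135) for combination therapy and 27.5% (39 of 142) for monotherapy". From the counts, 26/135 = 19.3% and 39/142 = 27.5%. Using these rates for this trial is an assumption, and they speak only to Week 6.
- Arm size: about 11 (SAP 3.4, 22 randomized).
- Response among sampled survivors, r: not in the documents. Assumed 50% to 90%.

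**Formulas** (m = mortality; T = combination, C = control; missing values due to death only)
- As written: difference = rT − rC.
- Death as not achieved: difference = (1 − mT)·rT − (1 − mC)·rC.

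**Equal survivor response in both arms**

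| r | As written | Death as not achieved (T vs C) | Difference |
|---|---|---|---|
| 50% | 0 | 40.4% vs 36.3% | 4.1 points |
| 60% | 0 | 48.4% vs 43.5% | 4.9 points |
| 70% | 0 | 56.5% vs 50.8% | 5.7 points |
| 90% | 0 | 72.7% vs 65.3% | 7.4 points |

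For r = 60%: 0.6 × (1 − 0.193) = 0.484 and 0.6 × (1 − 0.275) = 0.435.

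With the post hoc galactomannan subgroup of the same trial (17/108 = 15.7% versus 30/110 = 27.3%), the hidden difference is 5.8, 8.1 and 10.4 points at r = 50%, 70% and 90%.

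**When the sign reverses.** The two differences have opposite signs when (1 − mC)/(1 − mT) < rT/rC < 1. With 19.3% and 27.5% the lower limit is 0.898. For example, rT = 65% and rC = 70% give −5.0 points as written, but 52.5% versus 50.8% = +1.7 points with death as not achieved.

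**In whole subjects, 11 per arm (illustrative).** Deaths 1 versus 3 and responders 7 versus 6 give:
- all subjects: 7/11 versus 6/11 = 63.6% versus 54.5% = +9.1 points;
- with an observation: 7/10 versus 6/8 = 70.0% versus 75.0% = −5.0 points.

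**Scale.** One subject in 11 is 9.1 points, so 4.1 to 7.4 points is 0.45 to 0.81 of a subject. The subgroup maximum of 10.4 is just over one. A simple 95% interval for 43.5% versus 48.4% at 11 per arm has half-width 1.96 × √(0.435 × 0.565/11 + 0.484 × 0.516/11) ≈ 42 points.

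**The case against.** A reader might infer that a survival benefit itself could vanish or reverse. The documents do not support that. Overall survival (SAP 8.2.2) and all-cause mortality with a treatment difference (8.2.3) are analysed directly, and Global Response has a death category. Only the biomarker responder differences are exposed.

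A second tempting reading is that reversal should be expected. It needs lower response among survivors on the combination, which nothing in the documents establishes.

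The strongest counter-argument is that observed-case response is a legitimate choice for a biological marker. When survivors respond equally, a zero difference describes them correctly. The hidden points are the assumed mortality gap multiplied by r, and mortality is already reported. This stands as a description of what the observed-case figure means, and it is a reason to keep that figure. It does not make the figure a comparison of the arms as randomised, and the SAP does not present the rule as a deliberate choice.

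Two mitigations are real but partial. The Unknown or Missing row and the N in column headings make the loss visible, so all-subject percentages can be recomputed; the reported differences and CIs are still not corrected. SAP 8.2.6 counts subjects who reach the GMI targets, with those who die first censored but still in the percentage. That is cumulative to Day 84, covers GMI only, and requires two consecutive samples for the target below 0.5.

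It is also fair that the rule sits among table conventions and does not say at that visit. For a percentage reported by visit, that is the natural reading, and the ambiguity is one more reason to settle it in Section 8.

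**Conclusion.** The concern holds for the by-visit responder percentages of serum GMI, beta-D-glucan and PCR. Under the stated default they are survivor-selected comparisons, treating death differently from Global Response. The Week 6 illustration hides about 4 to 7 points, given the cited trial's primary-analysis mortality, equal survivor response of 50% to 90%, and losses through death alone. Weeks 1, 2 and 4 were not quantified, nor was loss through early stopping, which could work in either direction. At about 11 per arm the effect is less than one subject in that scenario and far inside the sampling error. It bears on bias in estimates meant to inform Phase 3, not on significance. No formal sample size rests on these endpoints, and two of the three are exploratory. The change should be made because it is cheap and the estimates will be reused.

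**What to change.** In SAP 8.2.5, 8.2.10 and 8.2.11 state:

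1. **Denominator:** all ITT subjects who meet the endpoint's baseline requirement. For GMI this is a serum value above 0 under Protocol 19.7.1.3, after reconciling it with the Protocol synopsis, which requires a positive baseline value. For beta-D-glucan and PCR it is a positive baseline result.
2. **Death, or discontinuation for lack of efficacy, before the visit:** not achieved.
3. **Other missing samples:** a separate rule, for example using the EoT sample when treatment ended early for success, so that these subjects are not counted as failures by default.
4. **Supportive table:** the observed-case percentage, stated to be among subjects with a value at that visit.

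The cost is SAP wording and one extra set of tables, with no new data. The percentages will look less favourable, and the main result becomes a composite of marker response and survival, which the table titles should say. SAP 3.7 places unblinding after database lock, so the change belongs before then. If lock has passed, add the analysis as a labelled sensitivity table.

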13.2.6. Footnotes

- A solid line spanning the margins will separate the body of the data display from the footnotes.
- All footnotes will be left justified with single-line spacing immediately below the solid line underneath the data display.
- Footnotes should always begin with “Note:” if an informational footnote, or 1, 2, 3, etc. if a reference footnote. Each new footnote should start on a new line, where possible.
- Subject specific footnotes are avoided, where possible.
- Footnotes will be used sparingly and add value to the table, figure, or listing. If more than six lines of footnotes are planned, then a cover page is strongly recommended to be used to display footnotes, and only those essential to comprehension of the data will be repeated on each page.

Statistical Analysis Plan

Sponsor: Scynexis, Inc.; Protocol No.: SCY-078-206

- The last line of the footnote section will be a standard source line that indicates the name of the program used to produce the data display, date the program was run, and the listing source (i.e., 'Program : myprogram.sas Listing source: 16.x.y.z').

14. Appendices

